Site PIs at CHOA, OHSU, and UMn met and agreed on all procedural details, including standards for usual care, led by [name]. A Manual of Procedures was created. Each site will obtain local IRB approval (central IRB not required for a K23). Data entry and collection will be centralized via a REDCap database built by [name].

The ECPI coordinator and [name] will provide data collection and entry training to the site PIs and coordinators.

Aim 1. Evaluate the preliminary efficacy of UrApp among caregivers of children with nephrotic syndrome in a pilot trial.

Participants and settings: 60 participants will be recruited from the nephrology clinics of CHOA,

OHSU, UMn, and MUSC. Sample size of 60 participants (randomized 1:1) will achieve 82% power to detect a 35% point difference in adherence with urine monitoring (primary outcome), with 20% drop-out. Sample size and power estimates are based on an adherence rate of 55% in the control group and 90% in the UrApp intervention group. These estimates are based on our single center experience with SOC⁸ and our experience with text messaging for NS monitoring, where 94% of the participants continued to check urine and provide results via text messaging at the end of 1 year (manuscript under review). Power was calculated using a two-sided Z-test with pooled variance at 0.05 type I error rate using PASS v. 14.0.8 (Kaysville, UT). Our sample size exceeds the recommended minimum of 12 participants per arm for pilot studies.²⁰

Inclusion criteria: Caregivers of patients ages 1-17 with steroid sensitive NS diagnosed within 42 days at time of enrollment; access to WIFI/internet; and proficiency with the English language.

Exclusion criteria: end-stage kidney disease; renal transplantation; and clinical or histologic evidence of secondary NS (e.g., systemic lupus erythematosus).

Procedures: Participants will be enrolled and randomized 1:1 to UrApp or SOC treatment arms at the baseline visit between 2-6 weeks after diagnosis. Recruitment will continue for 2 years, and participant follow-up will be 1 year. Written caregiver consent and patient assent (verbal for children ages 6-10 and written for children ages 11 and above) will be obtained per local IRB guidance.

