Figure 4. Urine protein monitoring questionnaire.

and urine protein logs (SOC arm) will also be collected to obtain the frequency of monitoring. *A priori*, we define adherence with urine protein monitoring as checking, on average, at least 2 times a week in the month preceding the assessment. Self-efficacy and QoL surveys will be administered in the same way as during the baseline visit. Relapse detection: patient medical charts will be reviewed for occurrence and frequency of delayed relapse reporting; defined as a relapse not reported to the treating physician until clinical manifestations or complications have occurred and/or only discovered during planned or unplanned visits or hospitalizations. Hospitalizations: medical records will be reviewed for the primary reason for admission and NS disease complications: bacterial peritonitis, septicemia, shock, blood clot(s), acute kidney injury, and seizures from hyponatremia or hypertension.

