 - a. Contact participant to see if they have any questions regarding the study or urine monitoring and screen for adverse events.
 - b. Remind participants to check their urine daily and contact the provider for any new disease relapses or remissions or medical concerns.
 - c. In case of adverse events (hospitalizations), see section below on "Adverse Event Reporting"
- 2. Confirm V2 date

UrApp Arm

- 1. Follow Appendix H. Phone Interview Template for Issues including UrApp Use
 - a. Contact participant to see if they have any questions regarding the study, urine monitoring, or using UrApp and screen for adverse events.
 - b. Remind participants to check their urine daily and contact the provider for any new disease relapses or remissions or medical concerns.
 - c. In case of adverse events, see section below on "Adverse Event Reporting"
- 2. Confirm V2 date
- 3. Research Staff only - Contact the Emory Study Staff for any technical issues, and Emory will reach out to the participants directly to resolve the issues.

Visit 2 (V2)

SOC Arm

- 1. Follow Appendix G. Phone Interview Template for Nephrotic Syndrome Monitoring Issues
 - a. Any questions regarding the study or urine monitoring and screen for adverse events.
 - b. Remind participants to check their urine daily and contact the provider for any new disease relapses or remissions or medical concerns.

- c. In case of adverse events, see section below on “Adverse Event Reporting”
 2. Hand out 2 bottles of urine test strips, check expiration date
 3. Administer surveys (Appendix E)
 - a. Self-Efficacy (Appendix E2)
 - b. PedsQL Parent Report (Appendix E3)
 - i. pick the appropriate patient age group: 2-4, 5-7, 8-12, 13-18
 - c. PedsQL Child Self Report (Appendix E4)
 - i. pick the appropriate patient age group: 5-7, 8-12, 13-18
 - e. Medication Adherence (Appendix E6)
 - f. Urine Testing Adherence (Appendix E7)
 4. Schedule V3
 5. Distribute stipend for \$20
- After the study visit:
6. Complete Hospitalizations and Relapses CRF (Appendix I)
 7. Complete V2 Data Entry on the Redcap Link

UrApp Arm

1. Follow Appendix H. Phone Interview Template for Issues including UrApp Use
 - a. Any questions regarding the study, urine monitoring, or using UrApp and screen for adverse events.
 - b. Remind participants to check their urine daily and contact the provider for any new disease relapses or remissions or medical concerns.
 - c. In case of adverse events, see section below on “Adverse Event Reporting”

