2. Hand out 2 bottles of urine test strips, check expiration date
3. Administer surveys (Appendix E)
 - a. Self-Efficacy (Appendix E2)
 - b. PedsQL Parent Report (Appendix E3)
 - i. pick the appropriate patient age group: 2-4, 5-7, 8-12, 13-18
 - c. PedsQL Child Self Report (Appendix E4)
 - i. pick the appropriate patient age group: 5-7, 8-12, 13-18
 - d. Medication Adherence (Appendix E6)
 - e. Urine Testing Adherence (Appendix E7)
 - f. UrApp Feedback Survey (Appendix E8)
4. OHSU,UMn, and MUSC only: Obtain best times for a Zoom interview with the Emory Research Staff from the participant within the upcoming 2 weeks
 - a. Discuss with the participant that the interview will likely take around 20 minutes and a \$50 stipend will be mailed to them
5. Distribute stipend for \$20
6. Emory site only – conduct participant interview (see below) and distribute stipend card for \$50
7. Schedule V3 date

After the study visit:

8. Complete Hospitalizations and Relapses CRF (Appendix I)

9. OHSU,UMn, and MUSC Research Staff only – contact Emory Research Staff for the best times for Emory to conduct the Zoom interview with the participants
10. Complete V2 Data Entry on the Redcap Link

Telephone/Virtual Option:

1. Research coordinator will call participants over Zoom for iPhone and Android (<https://www.doximity.com/clinicians/download/dialer>), so that research division's research phone number can be displayed instead of personal numbers of coordinators.
 - a. Coordinators will remind participants to check urine and call providers for disease relapses/remission.
 - b. During this call, participants will also be reminded to complete surveys and that they will be receiving urine test strips and a study stipend.
 - c. For participants in the UrApp Arm, a time will be set up to complete the interview.
2. RedCap link surveys will be sent via e-mail.
3. UrApp test strips will be mailed out.
4. Stipend (Clinicard or check) will be dispersed after receipt of completed surveys
5. Remind participants with phone calls to complete surveys once a week for up to 4 reminders.

For participants who are seen in clinic for a standard of care visit, the instructions can be provided via video conferencing, with the clinician setting up the video conferencing. Participants can also complete the surveys on paper while in clinic, and receive in person the urine test strips and stipend card from the clinician investigator.

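### The urine-testing survey follows a reminder to test at V2 and at the virtual V3, and its past-month window has no dates, so a primary outcome can partly record prompted behaviour and differs by visit mode

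*Combined protocol and SAP*

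**What the plan says.** All references are to the combined protocol and SAP.

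- **Outcome.** Section 2, Aim 1, Measures/Materials defines urine-monitoring adherence as "checking, on average, at least 2 times a week in the month preceding the assessment". Item 1 of the questionnaire (Figure 4) asks about the past month. Neither place ties that month to a visit or call date. UrApp data logs and paper urine logs (SOC arm) are also collected to give testing frequency, but the plan does not say whether survey or log decides the endpoint.
- **In-person V2, both arms (Section 4).** Step 1b reads: "Remind participants to check their urine daily and contact the provider for any new disease relapses or remissions or medical concerns". Step 2 hands out strips. Step 3 administers the surveys, including the urine-testing survey.
- **Virtual option, V2 and V3 (Section 4).** Step 1a reads: "Coordinators will remind participants to check urine and call providers for disease relapses/remission". Step 1b tells the family that strips are coming, step 2 e-mails the survey link, step 3 mails the strips, and step 5 reads: "Remind participants with phone calls to complete surveys once a week for up to 4 reminders". Aim 1 likewise allows four follow-up attempts within one month. No return cut-off is given.
- **In-person V3 (Section 4).** Step 1 asks only about serious illness or hospitalization, and step 2 is the surveys. The Section 3 tables tick the daily-testing instruction and the strip distribution at V2 but not at V3.

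**The concern.** The survey should describe testing in the month that led up to the 6- or 12-month assessment. The listed order can disturb this in two distinct ways.

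1. **Coloured self-report.** A family that has just been told to test daily is then asked how often it tested. The recalled month still precedes the prompt, but the answer may not be independent of it.
2. **Shifted window.** A virtual survey answered days or weeks after the call recalls a month that partly follows the reminder and the promised strips. This affects late virtual returns only.

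Reminders are also a component of the intervention (Table 1, function f). Prompting SOC families inside their measurement window gives them some of what the app supplies, and SOC has more room to rise on the plan's own rates. At 12 months virtual families are prompted and in-person families are not, so the two modes measure different things. The planned arm-by-time model has no term to separate this from a real change.

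**Working it through.** **1. The plan's own figure.** Section 2, Aim 1, Participants and settings gives the inputs: "Sample size of 60 participants (randomized 1:1) will achieve 82% power to detect a 35% point difference in adherence with urine monitoring", "with 20% drop-out", "based on an adherence rate of 55% in the control group and 90% in the UrApp intervention group", and a "two-sided Z-test with pooled variance at 0.05 type I error rate".

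- Evaluable: 60 × 0.80 = 48, or 24 per arm.
- The normal approximation gives 79.4% power. Exact binomial enumeration of the two-sided pooled Z-test gives 82.0%. The stated 82% therefore reproduces by the exact method, which is used below.

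**2. Share of the recalled month that follows the prompt.** Assumptions: a 30-day month, and weekly chases counted from the call. For a survey returned on day d, the share is min(d, 30)/30.

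| Return day | Share after the prompt |
|---|---|
| 0 | 0% |
| 7 | 7/30 = 23% |
| 14 | 14/30 = 47% |
| 21 | 21/30 = 70% |
| 28 | 28/30 = 93% |

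**3. Can this cross the threshold of two tests a week?** Take, purely as an illustration, a family testing once a week before the call and five times a week after it. Its 30-day average is (1 × (30 − d) + 5 × d)/30.

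- Day 7: (23 + 35)/30 = 1.93, not adherent.
- Day 14: (16 + 70)/30 = 2.87, adherent.
- Day 28: (2 + 140)/30 = 4.73, adherent.

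The same family is classed differently according to when it answers.

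**4. Effect on the contrast.** Let v be the share of families exposed and c the share of exposed non-adherent families who report as adherent, equal in both arms. The documents give neither value; c = 0.25 is assumed.

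- SOC = 0.55 + v × c × 0.45
- UrApp = 0.90 + v × c × 0.10
- Difference = 0.35 × (1 − v × c)

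| v | SOC | UrApp | Difference (points) | Exact power, 24 per arm |
|---|---|---|---|---|
| 0 | 55.0% | 90.0% | 35.0 | 82.0% |
| 0.25 | 57.8% | 90.6% | 32.8 | 78.5% |
| 0.50 | 60.6% | 91.2% | 30.6 | 74.7% |
| 1 | 66.3% | 92.5% | 26.2 | 66.1% |

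As listed, every family at V2 hears the reminder before answering. For those surveyed in person, however, only the colouring mechanism can act, and c may be well below 0.25. The last row is a ceiling for this value of c.

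**The case against.** Several objections have force.

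- **Scope.** Aim 1 makes in-person surveys the base procedure, and the virtual option also allows paper completion in clinic. In those cases the recalled month still ends at the prompt. This stands: the window shift belongs to late virtual returns alone.
- **Order.** The virtual list is not strictly chronological. Stipends after receipt (step 4) come before chasing (step 5), and the call itself reminds families to complete surveys, which may mean that the link is already out. Reminder first is the natural reading, but it is not stated outright. Either way, nothing requires the survey to come first.
- **Logs.** Dated logs could anchor the window whenever the survey returns. They could, but the plan does not say which source decides the endpoint.
- **Same prompt in both arms.** Families in both arms are told to test daily at baseline and reminded at V1, so the expected answer is known before V2. This limits the added colouring.

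A reader might infer that the procedure favours UrApp or raises the false-positive risk. The documents do not support that. The prompt is common to both arms, and bias between arms would need visit mode or return delay to differ by arm, on which the documents give no information. A reader might also infer that the measured month lies almost wholly after the prompt. That fits only a virtual return at about the fourth weekly chase (93%); at the third the share is 70%. Nor is a power of 66%, or the 45% obtained with c = 0.50 and v = 1, a forecast, since both assume that every family is exposed.

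**Conclusion.** The point holds as a weakness in how a primary outcome is measured. At in-person V2 the prompt and the strips precede the survey and can colour the answer. At virtual V2 and V3 a late return moves part or most of an undated recall month past the prompt. In-person V3 and the Section 3 tables carry no such reminder, so measurement at 12 months depends on visit mode, and the 6- and 12-month assessments are not like for like.

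The likely direction is a smaller arm contrast. The size is unknown because the documents give neither the virtual share, nor the distribution of return times, nor any prompt effect. Under the assumed 25% reporting shift, power is about 79% with a quarter of families exposed, 75% with half and 66% with all, against the planned 82%. The change is worth making because it is nearly free and makes the endpoint easier to interpret, even in a pilot of preliminary efficacy.

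**What to change.** 1. **Survey first.** At V2 and V3, in every mode and both arms, administer the medication and urine-testing adherence surveys before the reminder within the same contact, or send the virtual link before the call.
2. **Fix the window.** Print dates on Figure 4, item 1: the month ending the day before the scheduled V2 or V3 contact. This also covers families who have not answered by the time of the call. Record the completion date, and use the UrApp and paper logs for the same dates as a check.
3. **Reconcile V3.** The virtual V3 steps (reminder and strips) do not agree with in-person V3 or the Section 3 tables. The passages must be made consistent.

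Do not hold back strips or reminders until a survey returns. Home urine testing is how relapse is detected, and the steps above do not need any delay.

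**Cost.** Visit steps are reordered, and dates are added to one survey item. Late responders recall a slightly older month. The document is dated 17 February 2022 and recruitment was planned to run to March 2022, so some participants may already have been assessed under the existing order. Record which procedure applied to each assessment so that the two can be told apart in the analysis.

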For participants in the UrApp Arm, a Zoom invite will be sent over e-mail for the interview. The Zoom interview will be conducted by audio or video conferencing depending on participant choice and availability of webcams. The audio portion of the conferencing will be recorded, as outlined in the original protocol and consent form. After the interview is completed, the participant's stipend (Clinicard or check) will be dispersed.

Visit 3 (V3)

SOC Arm

1. Ask participants if their child has had any serious illnesses or hospitalizations.
 - a. In case of adverse events, see section below on "Adverse Event Reporting"
2. Administer surveys (Appendix E)
 - a. Self-Efficacy (Appendix E2)

UrApp Pilot Trial

- b. PedsQL Parent Report (Appendix E3)
 - i. pick the appropriate patient age group: 2-4, 5-7, 8-12, 13-18
 - c. PedsQL Child Self Report (Appendix E4)
 - i. pick the appropriate patient age group: 5-7, 8-12, 13-18
 - d. Medication Adherence (Appendix E6)
 - e. Urine Testing Adherence (Appendix E7)
 3. Distribute stipend for \$20.
- After the study visit:
4. Complete Hospitalizations and Relapses CRF (Appendix I)
 5. Complete V3 Data Entry on the Redcap Link

UrApp Arm

1. Ask participants if their child has had any serious illnesses or hospitalizations.
 - a. In case of adverse events, see section below on “Adverse Event Reporting”
2. Administer surveys (Appendix E)
 - a. Self-Efficacy (Appendix E2)
 - b. PedsQL Parent Report (Appendix E3)
 - i. pick the appropriate patient age group: 2-4, 5-7, 8-12, 13-18
 - c. PedsQL Child Self Report (Appendix E4)
 - i. pick the appropriate patient age group: 5-7, 8-12, 13-18
 - d. Medication Adherence (Appendix E6)
 - e. Urine Testing Adherence (Appendix E7)
 - f. UrApp Feedback Survey (Appendix E8)
3. OHSU, UMn, MUSC only: Obtain best times for a Zoom interview with the Emory Research Staff from the participant within the upcoming 2 weeks
 - a. Discuss with the participant that the interview will likely take around 20 minutes and a \$50 stipend card will be mailed to them
4. Distribute stipend for \$20
5. Emory site only – conduct participant interview (see below) and distribute stipend card for \$50
6. Collect loaned iPhone.

After the study visit:

7. Complete Hospitalizations and Relapses CRF (Appendix I)
8. OHSU, UMn, and MUSC Research Staff only – contact Emory Research Staff for the best times for Emory to conduct the Zoom interview with the participants

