- 3) The data trends are stored in the app and presented to users graphically and by calendar format. After performing a urine test, users can see at a glance recent urine protein trends and detect errors in UrApp interpretations. Data transmitted to the research staff will also include all the reading results to detect any errors in analysis.
- 4) The study staff will discuss with participants that UrApp requires internet connection/WiFi to send results via e-mail to the study staff. UrApp also includes the same notice upon starting app use. Failure to send the results e-mail will be instantly alerted to user. The app will also prompt result transmission on a monthly basis at a minimum. The study staff will query results monthly and will contact participants if results have not been received.
- 5) Participants will be instructed to contact their providers by telephone for any new disease relapse/remission. The research team will also contact the patient's provider if app results are received indicating new disease relapse/remission within 1 business day.
- 6) The research staff will contact participants at 1-3 months and 4-6 months to screen for app use issues. Contact information will also be provided to users should they have any technical issues.

Privacy / confidentiality: Patient demographic and clinical information will be captured from questionnaires and medical charts with potential for breach of confidentiality. Survey data and interview data will solicit participant perceptions and self-reporting of adherence, self-efficacy, and quality of life, and may intrude on their privacy. Lastly, transmission of urine protein results from the app to the research staff may also result in a breach of confidentiality. Safeguards to minimize privacy intrusion and breach of confidentiality, as outlined below:

- 1) Study ID will be assigned with patient identifiers stored separately in password-protected computers accessible only to study staff.
- 2) Survey results, clinical data collected from the medical charts will be de-identified, stored in a data-encryption system (REDCap) in password-protected computers, and accessible only to study staff.
- 3) Surveys administered electronically will utilize the secure, encrypted REDCap system.

- 4) Interview recordings will be digitally stored along with transcripts in password-protected computers accessible only to study staff.
- 5) Interviews will be conducted in private conference rooms without windows.

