- 6) Interviews will be conducted by trained research staff with field experience and understanding of respect for participant's privacy.
- 7) Participants using UrApp will be instructed to enter their Study ID as the identifier in the automatically generated e-mail containing the urine testing results, along with the sender's e-mail address. E-mail accounts set-up to receive data from UrApp will be created that are HIPAA-secure and accessible only to study staff.
- 8) The loaned iPhone for participants in the UrApp Arm without iPhones will be set up using an iTunes account created by the research team. The phone will be locked to the research team iTunes account so that participants cannot download other apps which may store personal information on the study iPhone. Thus, participant personal information will not be stored on the loaned iPhone. After the loaned phones are returned, the research staff will work with Emory IT department to ensure all participant information are deleted off the loaned iPhones.

Benefits

Study participants are not expected to directly benefit from the proposed research plan during study participation. However, they may find the prototype of the app to be helpful for their disease management. Their participation is expected to create a novel, pragmatic, and effective tool for nephrotic syndrome management, which can be used by the participants themselves and others in the future.

Safety Monitoring

1. Emory will review app transmitted results every business day, and report any new relapse/remission to the treating physician within 1 business day.
2. At planned study contacts, study staff will screen for any technical difficulties with UrApp. The study staff will also contact participants in the SOC arm for any questions regarding nephrotic syndrome management tasks in general (e.g. how to check urine for protein, what is the definition of a disease relapse) at the same planned study contacts. Any specific treatment concerns will be relayed to the treating physician.

Adverse Event Reporting

1. Screening for adverse events will be performed at each study contact, either by phone or in person.

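### The V3 visit steps and the virtual V2 and V3 lists ask for less than the schedule and Section 5 require, so non-serious harms after V2 risk being under-recorded

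*Combined protocol and SAP*

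**What the plan says.** Three parts of the protocol deal with adverse event screening.

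- **Section 5, Adverse Event Reporting.** Item 1: "Screening for adverse events will be performed at each study contact, either by phone or in person". Item 3 sends events that are not serious to the Adverse Event Form (Appendix J) at the follow-up visit. Under Safety Monitoring, item 2 adds: "At planned study contacts, study staff will screen for any technical difficulties with UrApp".
- **Section 3, schedule tables.** A row for screening for issues or adverse events is ticked at V1, V2 and V3 in both arms.
- **Section 4, visit steps.** V1 and V2 follow Appendix G (SOC) or Appendix H (UrApp) with a general screen. At V1 the SOC step is "Contact participant to see if they have any questions regarding the study or urine monitoring and screen for adverse events" and the UrApp step is "Contact participant to see if they have any questions regarding the study, urine monitoring, or using UrApp and screen for adverse events". At V3 both arms drop the template, and step 1 is "Ask participants if their child has had any serious illnesses or hospitalizations". The line under it begins "In case of adverse events, see section below on" and points to the reporting section. The telephone/virtual lists for V2 and V3 cover reminders, surveys, strips, stipends and interview scheduling, with no event question.

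Two smaller differences sit alongside. The V1 SOC routing line reads "In case of adverse events (hospitalizations), see section below on", while its UrApp counterpart has no parenthetical. Section 5, Potential Device Issues, item 6 says "The research staff will contact participants at 1-3 months and 4-6 months to screen for app use issues", whereas the Aim 1 procedures and the schedule put the second contact at 5-7 months.

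**The concern.** Coordinators work from the Section 4 steps. Someone following V3 step 1 literally asks a question that a family whose child had a non-serious problem can truthfully answer with no. Someone following only the virtual list asks nothing.

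The harms at issue are ones the protocol itself anticipates. Section 5, Potential Device Issues, says that app error could delay detection of relapse or remission and lists edema and cushingoid symptoms among the possible results. Either can occur without an admission. The data monitoring committee reviews safety every six months, and its view of later follow-up depends on what was asked at V3. A low count of non-serious events after V2 could then reflect the question and not the children.

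**Working it through.** The plan states no adverse event rate, so there is no figure of its own to reproduce. The check is a side-by-side reading followed by visit-window arithmetic.

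**1. What each source asks for**

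| Contact | Section 3 schedule | Section 4 arm steps | Section 4 virtual list |
|---|---|---|---|
| V1 | Screen ticked, both arms | General screen, both arms; SOC routing line adds the gloss | No separate list; V1 may be by phone |
| V2 | Screen ticked, both arms | General screen, both arms | No event question |
| V3 | Screen ticked, both arms | Serious illness or hospitalization only, both arms | No event question |

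Section 5 item 1 agrees with the schedule at every contact. The mismatch is at V3 in the arm steps, and at V2 and V3 in the virtual lists.

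**2. How long the V3 question covers**

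Inputs: V2 at 5-7 months and V3 at 11-13 months (Section 3).

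- Shortest interval: 11 − 7 = 4 months
- Longest interval: 13 − 5 = 8 months
- Nominal interval: 12 − 6 = 6 months, which is 6/12 = half of follow-up

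If a family is handled virtually at both V2 and V3, and the lists are taken as complete, the last event question was at V1 (1-3 months). The gap before V3 is then 11 − 3 = 8 to 13 − 1 = 12 months.

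**3. Child-time exposed to the narrower question**

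Inputs: 60 participants and 20% drop-out (Study Design, Aim 1).

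- All 60 followed: 60 × 6/12 = 30 child-years
- With 20% drop-out, all before V2: 60 × 0.8 = 48 children; 48 × 6/12 = 24 child-years

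These figures are for non-serious clinical events. App problems concern only the UrApp arm of 30, so the corresponding app time is 30 × 6/12 = 15 child-years, or 24 × 6/12 = 12 with drop-out.

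**4. Which named harms have another route**

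The outcome measures under Aim 1 have records reviewed in both arms for admissions and listed complications, including acute kidney injury and blood clots. Delayed relapse includes relapses that come to light through clinical manifestations, so edema that reveals an unreported relapse is captured there. The Hospitalizations and Relapses CRF is completed at V3 in both arms. No listed item covers cushingoid symptoms, or edema outside a delayed relapse. For those, the V3 prompt is the scheduled route.

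**The case against.** The strongest reply is that the protocol already requires the screen. Section 5 item 1 covers every contact by phone or in person, the schedule ticks V3, and the line under V3 step 1 speaks of adverse events without limiting them to serious ones. The virtual lists also omit the Hospitalizations and Relapses CRF, so they may be delivery notes added to the arm steps and not replacements for them. The contents of Appendices G, H, I and J are not available, so what those forms prompt for cannot be checked. All of this stands. It makes the fault an inconsistency and not a missing requirement, but it does not settle which text a coordinator will follow.

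Three stronger readings are tempting, and the documents do not support them.

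- *Non-serious harms after V2 go unrecorded.* Section 5 and the schedule require them to be sought and recorded. The supportable statement is that they risk being under-recorded.
- *The safety comparison is biased against the app.* This would rest on one parenthetical in a V1 routing line. The SOC step just above it tells staff to screen generally, V2 screening has no gloss in either arm, and V3 step 1 is identical by arm. The analysis paragraph plans no comparison of adverse events between arms; the clinical events it compares, delayed relapse and hospitalizations, come from chart review. The UrApp-only monthly results query, with contact of families who have not sent results, is a better reason to standardize prompts, but it does not demonstrate bias either.
- *App failures after V2 surface only if a family volunteers them.* Emory reviews transmitted results every business day, strip images travel with the readings, results are queried monthly, and V3 includes the UrApp feedback survey and an interview about barriers to use. The Safety Monitoring sentence on technical difficulties can also be read as meaning only the two contacts named under Aim 1, at months 1-3 and 5-7.

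**Conclusion.** The point holds as an internal inconsistency that should be corrected. V3 step 1 in both arms, and the virtual V2 and V3 lists, are narrower than Section 3 and Section 5. A site working from Section 4 would probably under-ascertain cushingoid symptoms, and edema outside a delayed relapse, over the 4 to 8 months before V3.

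The exposed time is up to about 30 child-years, or about 24 with drop-out. Both figures assume the nominal 6-month interval and that every site follows the Section 4 steps literally; the lower one also assumes that all drop-outs leave before V2. Section 4 mentions recruiting to replace up to 20%, which would move the total back toward 30. The number of events missed cannot be estimated, because the documents give no event rate.

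No planned efficacy analysis is affected. The V1 parenthetical is a wording fault that could narrow SOC reporting at that one visit. The 4-6 versus 5-7 month difference is a separate, minor consistency point.

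**What to change.** 1. In Section 4, Visit 3, replace step 1 in each arm with the V2 screening step: Appendix G for SOC, Appendix H for UrApp, with a screen for adverse events since V2.
2. Add the same step to the telephone/virtual lists for V2 and V3, or state that those lists supplement the arm steps.
3. In the V1 SOC routing line, delete the parenthetical so that both arms share one wording.
4. Reconcile the contact window in Section 5, Potential Device Issues, item 6 with the window in the Aim 1 procedures and the schedule.

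These are text changes that reuse existing templates at contacts already planned. The cost is a few extra minutes at V3 and at virtual visits, plus the amendment itself. For participants already past V3, the question cannot be asked at the planned time, so any report of non-serious events should state which wording was in use.
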